#### Serious Adverse Events

For the purpose of this study, admission to a hospital or freestanding residential facility for drug detoxification for the purpose of meeting eligibility criteria prior to randomization will not be

recorded as an SAE in the data system but will be documented in the source documentation as medically indicated. Such admissions would be reported to local IRBs per local IRB guidelines.

#### 11.25.4 Known Potential Toxicities of Study Drug/Intervention

Potential adverse events related to buprenorphine+naloxone (BUP, as Suboxone®) include: death, which has been reported among people who abuse BUP in combination with benzodiazepines and other drugs; withdrawal, if BUP is taken while actively taking methadone or various other opioids; increased risk of opioid dependence with continued use of heroin or other opioids; and possible impairment of mental or physical abilities for at least 6 hours after taking BUP.

Common side effects from BUP may include headache, constipation, difficulty sleeping, weakness, sleepiness, nausea, vomiting, sweating, and dizziness. Elevated liver enzyme levels have been reported in participants with hepatitis that are treated with buprenorphine.

As with any new medication, the long-term side effects of BUP are unknown at the present time.

Buprenorphine itself may cause physical dependence. It can also cause intoxication and mild respiratory depression, as evidenced by possible drowsiness and breathing that is slower and shallower.

If the participant attempts to dissolve and inject BUP, he/she may experience opioid withdrawal symptoms, including nausea, diarrhea, hot and cold sweats, hot flashes, muscle cramps, flushing, painful joints, yawning, restlessness, watery eyes, runny nose, chills, gooseflesh, sneezing, abdominal cramps, irritability, backache, tension and jitteriness, depression, sleepiness, shaking or tremor, sensitivity to noise, clammy or damp skin, or other unpleasant effects. Use of other opioids while receiving the BUP tablet could also result in opioid withdrawal symptoms.

Serious adverse reactions that may be associated with extended-release naltrexone by injection (XR-NTX; Vivitrol®) include: severe injection site reactions, eosinophilic pneumonia, allergic reactions, unintended precipitation of opioid withdrawal, accidental opioid overdose, depression and suicidality. Other adverse events seen in association with XR-NTX include hepatic enzyme abnormalities, nausea, and insomnia. Vivitrol® injections may be followed by pain, tenderness, induration, swelling, erythema, bruising, or pruritus; in some cases, injection site reactions may be very severe. In clinical trials, one participant developed an area of induration that continued to enlarge after 4 weeks, with subsequent development of necrotic tissue that required surgical excision. In the post-marketing period, additional cases of injection site reaction with features including induration, cellulitis, hematoma, abscess, sterile abscess, and necrosis, have been reported. Some cases required surgical intervention, including debridement of necrotic tissue, and some resulted in significant scarring.

In clinical trials of extended-release naltrexone by injection XR-NTX (Vivitrol®), there was one diagnosed case and one suspected case of eosinophilic pneumonia. Should a person receiving XR-NTX develop progressive dyspnea and hypoxemia, the diagnosis of eosinophilic pneumonia should be considered.

The most serious potential adverse effect of naltrexone is hepatocellular injury, which has almost always been associated with oral doses of 1400 to 2100mg per week. These doses result in much greater exposure to naltrexone than the 380mg/monthly dose of XR-NTX. At oral doses below 600mg/week, only relatively minor changes in liver tests have been reported and these have not been clearly attributed to naltrexone.

XR-NTX will precipitate or exacerbate opioid withdrawal in people dependent on opioids unless they have been opioid-free for 7-10 days. Any attempt to overcome the blockade produced by

XR-NTX by administering large amounts of opioids is very dangerous and may result in fatal overdose. Although XR-NTX blocks the effects of exogenous opioids for 28 days after administration, cases of opioid overdose with fatal outcomes have been reported in patients who used opioids at the end of a dosing interval or when missing a dose. Patients who have been treated with XR-NTX may respond to lower doses of opioids than previously used. This could result in potentially life-threatening opioid intoxication (respiratory compromise or arrest, circulatory collapse, etc.).

Patients taking XR-NTX may not benefit from opioid-containing medicines. Naltrexone antagonizes the effects of opioid-containing medicines, such as cough and cold remedies, antidiarrheal preparations and opioid analgesics

The commercial formulations of BUP (Suboxone®) and of XR-NTX (Vivitrol®) have been classified Pregnancy Category C. Female participants of childbearing potential will be required to practice acceptable birth control. Female participants will also be required to have a negative pregnancy test prior to the naloxone challenge and prior to administration XR-NTX and monthly thereafter while receiving medications.

# 12.0 DATA MANAGEMENT AND PROCEDURES

# **12.1** Design and Development

This protocol will utilize a centralized Data and Statistics center (DSC). The DSC will be responsible for the development of the case report forms (CRFs), development and validation of the clinical study database, ensuring data integrity, and training site and participating node staff on applicable data management procedures. Ideally, a web-based distributed data entry model will be implemented. This system will be developed to ensure that guidelines and regulations surrounding the use of computerized systems used in clinical trials are upheld. The remainder of this section provides an overview of the data management plan associated with this protocol.

# **12.2** Operations Manual

An operations manual will be provided for this study that incorporates procedures from this protocol with those procedures necessary for the day-to-day conduct of the trial. The operations manual will be used to train study staff, to provide reference for study procedures, and to support quality management activities.

# **12.3** Site Responsibilities

The data management responsibilities of each individual CTP will be specified by the DSC.

# **12.4** Data Center Responsibilities

The DSC will 1) develop a data management plan and will conduct data management activities which include, but are not limited to, method for ensuring subject confidentiality in the database, 2) provide final paper CRFs and eCRFs with instructions for the collection of all data required by the study, 3) provide data dictionaries for each paper CRF and eCRF that will comprehensively define each data element, 4) conduct ongoing data validation and cleaning activities on study data from all participating CTPs through database lock.

# 12.5 Data Collection

Data will be collected at the study sites either on source documents, which will be entered at the site into eCRFs or through direct electronic data capture. The eCRFs will be supplied by the DSC. eCRFs are to be completed on an ongoing basis during the study. The medical chart and the source documents are the source of verification of data. Paper CRFs and eCRFs should be completed according to the CRF instruction manual and relevant instructions in the study operations manual.

# **12.6** Data Acquisition and Entry

Completed forms and electronic data will be entered into the data management system in accordance with the CRF Completion Guidelines established by the DSC. Only authorized individuals shall have access to electronic CRFs.

# **12.7** Data Editing and Control

Data will be entered into the DSC automated data acquisition and management system. If incomplete or inaccurate data are found, a data clarification request will be generated and distributed to treatment programs for a response. Sites will resolve data inconsistencies and errors and enter all corrections and changes into the DSC automated data acquisition and management system. Data status reports will be issued on a regular basis to assist the site, the

corresponding RRTC (node) and the lead investigator to monitor the site's progress in responding to queries.

Participating investigators agree to routine data audits conducted by DSC staff. Monitors will routinely visit each site to assure that data entered on the appropriate eCRFs are in agreement with source documents. They will also verify that investigational products have been properly stored and accounted for, participant informed consent for study participation has been obtained and documented, all essential documents required by GCP regulations are on file, and sites are conducting the study according to the research protocol. Any inconsistencies will be resolved, and any changes to the data forms will be made using the established procedures specified in the study operations manual.

When the study is completed and all data have been entered into the clinical database and the database has been checked by Quality Assurance and is locked, statistical analysis of the data will be performed by the DSC's statisticians in accordance with the analytical plan section of this protocol.

# **12.8** Study Documentation and Records Retention

Study documentation includes all data correction forms, workbooks, source documents, monitoring logs and appointment schedules, Sponsor correspondence and regulatory documents (e.g., signed protocol and amendments, Ethics or Institutional Review Committee correspondence and approved consent form and signed participant consent forms, Statement of Investigator form, and clinical supplies receipt and distribution records, among others).

Source documents include all recordings of observations or notations of clinical activities and all reports and records necessary for the evaluation and reconstruction of the clinical research study. Accordingly, source documents include, but are not limited to, laboratory reports, ECG tracings, X-rays, radiologist reports, participant diaries, biopsy reports, ultrasound photographs, participant progress notes, hospital charts or pharmacy records and any other similar reports or records of any procedure performed in accordance with the protocol.

Government agency regulations and directives require that the investigator must retain all study documentation pertaining to the conduct of a clinical trial. In an IND study, these documents must be kept for a minimum of two years after discontinuation of the IND, 3 years after the approval of the NDA, or as directed by the study sponsor.

#### 12.9 Data Transfer/Lock

Data will be transmitted by the DSC to the NIDA central data repository as requested by NIDA. The DSC will conduct final data quality assurance checks and "lock" the study database from further modification. The final analysis dataset will be returned to NIDA and the lead investigator, as requested, for storage and archive.

# 12.10 Data Training

The training includes provisions for training on assessments, CRF completion guidelines, and computerized systems.

# 12.11 Data QA

To address the issue of data quality, the DSC will follow a standard data monitoring plan. An acceptable data quality level prior to any database lock will be given as part of the data management plan. Data quality summaries will be made available during the course of the study.

#### 12.12.2 Confidentiality of Participant Records

To maintain participant confidentiality, all laboratory specimens, eCRFs, reports and other records will be identified by a participant identification code that includes the site number, node number, and participant number. Research and clinical records will be stored in a locked cabinet. Only research staff and NIDA program officials will have access to the records. Participant information will not be released without written permission, except as necessary for monitoring by the FDA if under IND, the NIDA monitoring contractor, or NIDA.

By signing the protocol the investigator agrees that within local regulatory restrictions and ethical considerations, NIDA or any regulatory agency may consult and/or copy study documents in order to verify eCRF data.

# 13.0 PUBLICATIONS AND OTHER RIGHTS

Per NIH policy, the results of the proposed trial are to be made available to the research community and to the public at large. The planning, preparation, and submission of publications will follow the policies of the Publications Committee of the CTN.

# **APPENDIX A**

# Adverse Event Reporting Definitions and Procedures

Each participating site's principal investigator is responsible for study oversight, including ensuring human research subject protection by designating appropriately qualified and trained study personnel to assess, report, and monitor adverse events.

# Definition of Adverse Events and Serious Adverse Events

An **adverse event** (AE) is any untoward medical occurrence in humans, whether or not considered study drug/intervention related which occurs during the conduct of a clinical trial. Any change from a baseline pre-existing condition based on clinical status, ECGs, lab results, x-rays, physical examinations, etc., that is considered clinically significant by the study medical clinician are considered AEs.

**Suspected adverse reaction** is any adverse event for which there is a reasonable possibility that the study drug/intervention caused the adverse event. A reasonable possibility implies that there is evidence that the study drug/intervention caused the event.

Adverse reaction is any adverse event caused by the study drug/intervention.

An **adverse event, suspected adverse reaction,** or **adverse reaction** is considered "**serious**" (i.e. a serious adverse event, serious suspected adverse reaction or serious adverse reaction) if, in the view of either the study medical clinician or sponsor, it:

- 1. Results in death: A death occurring during the study or which comes to the attention of the study staff during the protocol-defined follow-up period, whether or not considered caused by the study drug/intervention, must be reported.
- 2. Is life-threatening: Life-threatening means that the study participant was, in the opinion of the medical clinician or sponsor, at immediate risk of death from the reaction as it occurred and required immediate intervention.
- 3. Requires inpatient hospitalization or prolongation of existing hospitalization.
- 4. Results in persistent or significant incapacity or substantial disruption of the ability to conduct normal life functions.
- 5. Is a congenital abnormality or birth defect.
- 6. Important medical event that may not result in one of the above outcomes, but may jeopardize the health of the study participant or require medical or surgical intervention to prevent one of the outcomes listed in the above definition of serious event.

#### Definition of Expectedness

Any adverse event is considered "unexpected" if it is not listed in the investigator brochure or the package insert or is not listed at the specificity or severity that has been observed. If neither is available then the protocol and consent are used to determine an unexpected adverse event.

#### Pregnancy

Any pregnancies that occur to a participant enrolled in the study will be captured on a pregnancy CRF and not separately reported as an AE or SAE. Women who become pregnant

during the active treatment period will be discontinued from further medication administration, referred for medical care, and the pregnancy followed until an outcome is known.

#### Medical and Psychiatric History

A thorough medical and psychiatric history during the screening phase should record any chronic, acute, or intermittent preexisting or current illnesses, diseases, symptoms, or laboratory signs of the participant, to avoid reporting pre-existing conditions as new AEs and to assist in the assessment of worsening in intensity or severity of these conditions that would indicate an AE. Stable chronic conditions, such as arthritis, which are present prior to clinical trial entry and do not worsen are not considered AEs.

#### Site's Role in Eliciting and Reporting Adverse Events

Appropriately qualified and trained medical personnel will elicit participant reporting of AEs and SAEs at each study visit designated to collect AEs. Adverse events (medical and/or psychiatric) assessment will initiate with participant consent and follow-up will continue through 30 days post last study visit. Medical personnel will obtain as much information as possible about the reported AE/SAE to complete the AE/SAE forms and will consult as warranted.

Standard reporting, within 7 days of the site becoming aware of the event, is required for reportable AEs. Expedited reporting (within 24 hours of their occurrence and/or site's knowledge of the event) is required for reportable SAEs (including death and life-threatening events). Local sites are responsible for reporting SAEs to their IRB, per their IRB's guidelines.

Sites are required to enter reportable AEs and SAEs in the AdvantageEDC system. The AE form is used to capture reportable AEs (as defined in the protocol). Additional information may need to be gathered to evaluate serious adverse events and to complete the appropriate CRFs and the summary. This process may include obtaining hospital discharge reports, medical records, autopsy records or any other type records or information necessary to provide a complete and clear picture of the serious event and events preceding and following the event. If the SAE is not resolved or stable at the time of the initial report or if new information becomes available after the initial report, follow-up information must be submitted as soon as possible.

Reportable adverse events will be followed until resolution, stabilization or study end. Any serious adverse reactions will be followed until resolution or stabilization even beyond the end of the study.

#### Site's Role in Assessing Severity and Causality of Adverse Events

Appropriately qualified and trained medical personnel will conduct an initial assessment of seriousness, severity, and causality when eliciting participant reporting of adverse events. A study medical clinician will review reportable AEs for seriousness, severity, and causality on at least a weekly basis.

#### **Guidelines for Assessing Severity**

The severity of an adverse event refers to the intensity of the event.

Grade 1	Mild	Transient or mild discomfort (< 48 hours), no or minimal medical intervention/therapy required, hospitalization not necessary (non-prescription or single-use prescription therapy may be employed to relieve symptoms, e.g., aspirin for simple headache, acetaminophen for post-surgical pain)
Grade 2	Moderate	Mild to moderate limitation in activity some assistance may be needed; no or minimal intervention/therapy required, hospitalization possible.
Grade 3	Severe	Marked limitation in activity, some assistance usually required; medical intervention/ therapy required hospitalization possible.

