#### 8.2.4 Electrocardiogram (ECG)

A 12-lead ECG will be administered by appropriately qualified and trained medical personnel. The screening ECG will assist in determining participant eligibility. The ECG will be repeated at week 5, and at the end-of-medication visit (if medication is stopped early) or at the end-of-treatment visit (last visit of Week 8).

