#### 8.2.5 Clinical Laboratory Tests

A comprehensive blood chemistry including liver function tests (LFTs: including AST, ALT, GGT, ALP, and bilirubin), PT w/INR (Prothrombin Time/International Normalized Ratio) and PTT (Partial Thromboplastin Time), a hematology panel, and a standard urinalysis will be performed to help determine eligibility at screening. Although receipt of laboratory test results is not necessary before conducting the naloxone challenge, the lab results must be received and reviewed prior to administration of XR-NTX.

At screening, hepatitis B and C serology tests will be conducted including hepatitis B surface antigen (HBs Ag), hepatitis B surface antibody (Anti-HBs), hepatitis B core IGM antibody (Anti-HBc), hepatitis C virus antibody (HCV Ab), and HIV testing.

Clinical lab tests will also be repeated in the study week prior to the second XR-NTX administration, and at the end-of-medication visit (if medication is stopped early) or at the end-of-treatment visit (last visit of Week 8).

A central laboratory that is accredited by the College of American Pathologists (CAP) or equivalent, and participates in the Clinical Laboratory Improvement Act of 1998 (CLIA) will perform these analyses. The central laboratory will provide normal values and proof of lab certifications.

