#### 10.9 Safety Analysis

Adverse events (AEs), including serious adverse events (SAEs), will be summarized by body system and preferred term using MedDRA (The Medical Dictionary for Regulatory Activities). Adverse events will be presented in two ways: (1) the number and proportion of participants experiencing at least one incidence of each event will be presented overall and by treatment group; and (2) a table displaying the total number of each event will be given overall and by treatment group. Listings of serious adverse events will be given, sorted by treatment, body system, and preferred term. Detail in these listings will include severity, relationship to study drug, and action taken as available. Treatment arm differences will be monitored by the DSMB.

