#### **11.25.3** Reportable Adverse Events and Serious Adverse Events

#### Adverse Events

For the purpose of this study, the following AE will not require reporting in the data system but will be captured in the source documentation as medically indicated:

• Grade 1 (mild) adverse events

This would typically include mild physical events such as headache, cold, etc., that were considered not reasonably associated with the use of the study drug/intervention.

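### The severity scale has no laboratory or ECG criterion, so silent liver-enzyme or QTc changes may be graded mild by default and missed by the by-arm safety tables

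*Protocol*

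**What the plan says.** **Grading (Appendix A, Guidelines for Assessing Severity).** Grade 1 is "Transient or mild discomfort (< 48 hours), no or minimal medical intervention/therapy required, hospitalization not necessary". Grade 2 is "Mild to moderate limitation in activity some assistance may be needed; no or minimal intervention/therapy required, hospitalization possible". Grade 3 is "Marked limitation in activity, some assistance usually required; medical intervention/ therapy required hospitalization possible".

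**Reporting (11.25.3, Adverse Events).** The section says that "the following AE will not require reporting in the data system but will be captured in the source documentation as medically indicated". One bullet follows, naming Grade 1 (mild) events without qualification. The sentence after the bullet describes the typical content as minor physical complaints judged unrelated to the study drug. Appendix A (Site's Role in Eliciting and Reporting Adverse Events) has sites enter the events that the protocol defines as reportable.

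**Definition (Appendix A).** A change from baseline in a laboratory result or ECG is an adverse event if the study medical clinician considers it clinically significant. An important medical event can be serious whatever its effect on activity.

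**Analysis.** Section 10.9 says: "Adverse events (AEs), including serious adverse events (SAEs), will be summarized by body system and preferred term using MedDRA". It plans two by-arm tables, one of participants with at least one of each event and one of total event counts, plus listings of serious events. Secondary objective 1 in 4.2.2 measures safety by adverse events.

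**Data collected.** From 8.2.5: "Clinical lab tests will also be repeated in the study week prior to the second XR-NTX administration", with a further set at the end of medication or treatment. From 8.2.4: "The ECG will be repeated at week 5, and at the end-of-medication visit", or at the end-of-treatment visit for those who complete.

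**Effects expected.** Section 11.25.4 says of buprenorphine: "Elevated liver enzyme levels have been reported in participants with hepatitis that are treated with buprenorphine". It also lists hepatic enzyme abnormalities for XR-NTX. QTc prolongation is an exclusion in 5.3.2 and the reason for barring some co-medications in 7.4.1. It is not among the toxicities listed in 11.25.4.

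**The concern.** Liver-enzyme rises and QTc prolongation are often found by measurement and not by complaint. A scale built on symptoms gives the site no usable instruction for them, and the lowest grade is the natural default. That grade is also the one that need not be entered. An effect the protocol anticipates could therefore be measured on schedule, recognised by the clinician, recorded in the source notes, and still not be counted in the by-arm tables.

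Safety is half of the stated aim, and the adverse-event tables are its named measure. Grading and data entry happen at sites during conduct, so an analysis plan cannot restore an event that was never entered.

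**Working it through.** No figure in the plan needs reproducing. The check follows one case through the written rules: a liver-enzyme rise or QTc prolongation on treatment that the clinician considers clinically significant, with no symptoms and no treatment given.

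1. **Is it an adverse event?** Yes, by the Appendix A definition, because the clinician considers it significant.
2. **Is it serious?** Only if it meets a seriousness criterion. The important-medical-event criterion is open to it, but by judgement, with no threshold stated.
3. **Which grade?** Grade 3 needs marked limitation of activity and medical intervention, and neither is present. Grade 2 needs mild to moderate limitation, which is absent. Grade 1 describes short or mild discomfort lasting under 48 hours. The finding is not discomfort, and with one scheduled panel in Week 4 and one at the end, its duration would usually be unknown. No grade fits. Grade 1 is nearest because it asks for the least.
4. **Is it entered?** If graded 1, the answer turns on how 11.25.3 is read. The bullet exempts every Grade 1 event. The sentence after it points to events unrelated to study drug, but only as what is typical. Two sites could read this differently and both claim compliance.
5. **Is it in the tables?** Section 10.9 counts events by body system and preferred term, not by severity. An entered event counts whatever its grade. An event that is not entered does not count. The loss therefore arises at step 4, and the grade matters because it decides step 4.

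**Measurements at stake.** The planned sample is 300 (5.3). Table 2 schedules two post-randomization liver panels (Week 4; end of medication or treatment) and two ECGs (Week 5; end of medication or treatment).

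- Liver panels: 300 × 2 = 600, or 100 × 2 = 200 per arm.
- ECGs: 300 × 2 = 600, or 200 per arm.

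These are full-attendance figures. The screening measurements (another 300 of each) are before randomization and serve as baseline.

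**Effect on the comparison.** Let *e* be the share of such events that sites enter. If *e* is the same in all arms, the expected by-arm difference in the tables is *e* × (true difference). The protocol does not fix *e*. It could lie anywhere from 0 to 1 and may vary by site.

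**What the collected values could show.** The protocol gives no event rates, so these are assumptions. With 100 per arm and a two-sided Fisher exact test at 5%, exact power for a marked rise is:

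| Control | Buprenorphine arm | Power |
|---|---|---|
| 5% | 10% | 0.19 |
| 5% | 15% | 0.59 |
| 5% | 20% | 0.88 |

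Only large contrasts would be seen reliably even with complete data, so there is little room to lose cases. The point does not rest on these rates.

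**The case against.** The other side has a good deal to say.

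- **The protocol does not grade these findings mild.** A reader might infer that it does and that they therefore drop out. The text does not support that. It gives no rule for them, the section is headed as guidelines, and a clinician may choose a higher grade. This stands, and it limits the claim to what may happen.
- **Severity does not shape the by-arm tables.** A reader might infer that the scale alone would hide a signal, even if mild events were entered. Section 10.9 plans no by-arm table by severity, so entry would be enough for an event to be counted. This stands.
- **There are other routes to entry.** A clinician can call the finding an important medical event, which makes it serious and reportable. The explanatory sentence in 11.25.3 can be read as keeping drug-related mild events reportable. Both routes are real. Both depend on individual judgement, and the second depends on which of two adjacent statements a site follows.
- **Oversight exists.** A medical monitor reviews safety data and presents them to the DSMB (11.25.1). This helps with serious events, but the protocol does not say that ungraded or unentered laboratory changes reach that review.
- **Tables of values are normally left to an analysis plan.** This is correct. Section 10.3 calls 10.9 an outline, and nothing in the protocol discards the values. Section 12.7 does tie the analysis to the protocol's own analytical section, but that does not forbid further summaries. The absence of such tables is not counted as an error here.
- **Differing baselines are partly covered.** Participants may enter with liver tests up to 5 times the upper limit (5.3.2), but Appendix A asks for pre-existing laboratory signs to be recorded so that worsening can be judged. This largely stands.
- **The expected signals are limited.** The buprenorphine liver statement concerns participants with hepatitis, every arm receives XR-NTX, and QTc is not a listed toxicity. The hepatic case is thus stronger than the QTc case.

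The copy read shows Grades 1 to 3. Higher rows may be missing from it, and nothing here depends on them.

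**Conclusion.** The point holds as a gap in two rules that the protocol itself fixes. The grades shown cannot classify a significant but silent laboratory or ECG change, and 11.25.3 states the mild-event exemption in two ways that do not agree. Together they allow such a change to be graded mild by default, left out of the data system, and so left out of the by-arm tables in 10.9. The documents do not show that this will happen in every case.

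The share lost could be anything from none to all, depending on how sites grade and how they read 11.25.3. The underlying measurements, about 600 liver panels and about 600 ECGs on treatment at full attendance, remain available. What can be lost is the adverse-event record, which is the measure that secondary objective 1 names. The conclusion assumes that sites apply the protocol's wording and have no other grading instruction, such as one in the operations manual. The change is worth making because it is cheap and uses data already collected.

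**What to change.** 1. **Appendix A, Guidelines for Assessing Severity.** State that laboratory and ECG adverse events are graded on a named, recognised value-based scale that takes account of the participant's screening value, and not by activity limitation.
2. **Section 11.25.3.** State that clinically significant laboratory or ECG changes, and any event judged related to study drug, are entered in the data system whatever their grade. This reconciles the bullet with the sentence that follows it.
3. **Section 10.9 (supporting change).** Name by-arm summaries of the liver-test and QTc values already collected, each set against the screening value.

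The cost is a paragraph in Appendix A, a sentence in 11.25.3, two more tables, and somewhat more adverse-event entry at sites. No test, visit, eligibility criterion or treatment rule changes. Items 1 and 2 work best before enrolment starts. If enrolment is under way, sites would need to review source notes for Grade 1 laboratory and ECG findings already left out.
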